**Variables:**

The main exposure of interest will be the use of upadacitinib. Other select systemic AD treatments may consist of azathioprine, ciclosporin, dupilumab, methotrexate and mycophenolate mofetil. The

variables studied as outcomes will be malignancy (excluding NMSC) including malignancy by type, NMSC, MACE, VTE, serious infections (including OI), HZ, EH/KVE, active TB, GI perforations, DILI, fractures, and all-cause mortality. In addition to exposures and outcomes, other baseline variables, possible confounders and effect modifiers will be included in the study. These variables will include demographics, socioeconomics, proxy measures for lifestyle factors, comorbidities, past and present medication use, and past medical procedures. As a proxy measure of disease severity, healthcare utilization before cohort entry will be considered.

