## 9. Research Methods

### 9.1. Study Design

The study is based on data from the nationwide health and administrative registers from Denmark and Sweden, covering country populations of approximately 5.8 million and 10.2 million people, respectively. It is a longitudinal, non-interventional, population-based, register-based cohort study of adolescents and adults with AD exposed to upadacitinib or other select systemic AD treatments, identified in the Danish and Swedish nationwide registers.

Importantly, labelling changes following Article 20 procedure are likely to result in substantial differences in baseline characteristics of patients initiating upadacitinib and those initiating other systemic treatments. Therefore, initial in-depth descriptive analyses will be conducted to assess comparability across treatment cohorts and inform the design (including selection of suitable comparator/s) of subsequent analyses.

The select systemic AD treatments (including biosimilars) evaluated as potential comparator treatments in the study are:

- Azathioprine
- Ciclosporin
- Dupilumab
- Methotrexate
- Mycophenolate mofetil

ATC codes and procedure codes for the comparator treatments are listed in Annex 3. Additional Information, [Table 3.2](#). Additional upcoming marketed AD treatments may become relevant as comparator treatments as the study progresses. Therefore, the list may be extended to cover

other available and approved AD treatments in Sweden and Denmark during the study period. Final codes and definitions will be specified in the Statistical Analysis Plan (SAP) before data extraction for interim analysis and final analysis.

A *new user*, active comparator design will be used to address the objectives of the study. *New user* is defined as not having used that specific drug substance in the year (12 months, 365 days) before the first eligible treatment.

The first dispensed prescription/administration date of upadacitinib or one of the comparator treatments within the study period (see definition in Section 9.2.2. ), will be defined as the *index date*.

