## 9.2. Setting

### 9.2.1. Source Population, Study Population and Study Cohort

The *source population* will be all individuals with at least one diagnosis of AD (ICD-10 code L20) as registered in the Danish and Swedish patient registers since 1998 (the year when ICD-10 was fully implemented in both countries).

To be eligible for inclusion into the *study population* and the *study cohorts* individuals must:

- have a recorded diagnosis of AD
- have at least one dispensed prescription/administration of upadacitinib or one of the select systemic AD treatments within 12 months from the AD diagnosis during the *study period* (see definition in Section 9.2.2. )
- be a *new user* of either upadacitinib or one of the select systemic AD treatments at *index date*
- be  $\geq 12$  years old at the *index date*
- have at least 12 months' continuous residency in the respective country (Denmark or Sweden) prior to the *index date*
- For the potential comparator cohorts, have at least one dispensed prescription/administration of another systemic AD treatment before *index date*

The following exclusion criteria apply to the study population:

- Individuals who used other JAK inhibitors (e.g. tofacitinib, baricitinib, abrocitinib) at any time (all available lookback time) before the *index date* will be excluded

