**Table 1 Baseline Variables**

Data type	Description
Demographics and socioeconomics	Age Sex Education Income Occupation Region of residency
Lifestyle factors	Smoking (identified through proxies) Alcohol use (identified through proxies)
Medical history within 5 years prior to index date	Asthma Obesity Hypertension Hyperlipidemia Diabetes Myocardial infarction Stroke Peripheral vascular disease Rheumatoid arthritis Depression Anxiety Insomnia Chronic obstructive pulmonary disease (COPD) Moderate hepatic impairment Serious infection Active TB Atherosclerotic cardiovascular disease Malignancy Chronic infection with hepatitis B virus (HBV) or hepatitis C virus (HCV) Severe renal impairment Endogenous uveitis Nephrotic syndrome Transplantation (organ/bone marrow) Psoriasis Crohn's disease Ulcerative colitis Celiac disease Acute lymphocytic leukemia (ALL) Systemic lupus erythematosus (SLE) Polymyositis and dermatomyositis Pemphigus Polyarteritis nodosa Autoimmune hemolytic anemia Chronic Idiopathic (Immune) Thrombocytopenic Purpura Polyarticular Severe Active Juvenile Idiopathic Arthritis External Otitis Previous fracture
Medication use within 1 year prior to index date	Antihypertensives Lipid-lowering drugs Antidepressants Anxiolytic drugs Antipsychotics Insomnia medications

Use of AD treatments other than the ones being studied within 1 year prior to index date	Biologic Non-biologic systemics Phototherapy Topical agents
Healthcare utilization as proxies of AD severity within 1 year prior to index date	Number of AD inpatient days at baseline Number of AD outpatient visits at baseline Number of non-AD inpatient days at baseline Number of non-AD outpatient visits at baseline

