### 9.7.1. Descriptive Analysis

All descriptive statistics will be presented separately for Sweden and Denmark. Mean (standard deviation [SD]) and median (25th percentile, 75th percentile) will be used as descriptive statistics for continuous variables and counts and proportions for categorical variables.

Descriptive analyses will be conducted to characterize the users and the real-world utilization of upadacitinib and other select systemic AD treatments to assess suitability of treatment groups as potential comparators to the upadacitinib cohort. These descriptive analyses will provide guidance on potential comparators and feasibility of comparing incidence rates across treatment cohorts.

Drug utilization and individual baseline characteristics (e.g.; demographics, comorbidities, concomitant treatments, treatment experience, healthcare utilization) will be summarized for upadacitinib and select systemic AD treatments, separately for each country, by dose (upadacitinib), age group at initiation, relevant risk factors (e.g., malignancy, VTE, and MACE), and disease history as listed in the secondary objectives (moderate hepatic impairment, hepatitis B & C, severe renal impairment).

PS will be generated for upadacitinib users and other select systemic AD treatments users [55-57]. The distribution/overlap of propensity scores will be examined to assess the balance across cohorts. The SMD will be used to assess comparability across treatment groups if needed.

Person-years at risk and the number of safety outcomes for upadacitinib will be reported overall and across risk factor strata, crude incidence rates for upadacitinib will be presented. If suitable/comparable treatment cohorts can be identified, crude incidence rates for all safety outcomes will be provided for other select systemic AD treatments, as well.

Descriptive analyses will be performed in the interim report and the final report.

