### 9.7.2. Comparative Analysis

[REDACTED] analyses will be performed to compare upadacitinib and comparator treatments in the final report.

Comparisons of rates of safety outcomes between upadacitinib and comparator cohorts will be made with Cox proportional hazard regression models using appropriate strategies such as IPTW, PS matching/ stratification/ adjustments or others to achieve comparable balance across cohorts.

[Table 7](#) below specifies the exposure definitions that will be used as time at risk for each outcome.

With the ITT exposure definition, individuals will be considered exposed to the first eligible treatment received until the end of follow-up while with the modified ITT individuals will be considered exposed to the first eligible treatment received and censored at treatment switching. With both ITT and modified ITT, Cox proportional hazards regression models with treatment group (upadacitinib, comparator) as exposure will be performed. For malignancy, exposure time and time to event will start to be counted from the lag-time (for main analysis 12 months) from index date.

With the time-varying exposure definition individuals may change exposure status when starting different treatments, and thus the treatment covariate is time-varying. Cox proportional hazards regression models with treatment group (upadacitinib, comparator, unexposed time, concomitant use/switch) as covariate will be performed. The time scale in the models will be time since start of the treatment group, i.e., time since beginning of the exposure to the specific treatment group (upadacitinib, comparator, unexposed time, concomitant use/switch).

The hazard ratio (HR) and 95% confidence interval (CI) will be reported from the Cox models. Kaplan-Meier curves for all outcomes will also be reported. In addition, 5-years overall survival rate will be presented for malignancy excluding NMSC, NMSC, MACE and all-cause mortality as well as 5-years event-free survival rates for malignancy excluding NMSC, NMSC and MACE.

Analyses will be performed based on pooled individual data, unless legal barriers towards transfer of individual data make it impossible, in which case meta-analyses of aggregated data will be performed instead. Methods for meta-analysis will be described in the SAP and the barriers for data pooling will be assessed in connection with the interim report.

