**9.7.2.1. Sensitivity Analysis and Subgroup Analysis**

Sensitivity analyses for all safety outcomes will be performed among individuals in the study population with no prior use of any of the other systemic AD treatments within 12 months from *index date*. Sensitivity analyses with 0- and 6-months lag time for malignancy outcomes will be conducted.

In addition, subgroup analyses will be performed by upadacitinib dose, age group, relevant risk factors (e.g., malignancy, VTE, and MACE) and disease histories as listed in the secondary objectives.

Details on the sensitivity and subgroup analyses for all safety outcomes will be described in the SAP.

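### Section 9.2.1 requires an earlier systemic AD treatment of comparators only, so systemic-naive upadacitinib users have no counterpart in the comparison, and no listed baseline variable secures adjustment for treatment line

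*Protocol*

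**What the plan says.** The criterion common to both sides in Section 9.2.1 is new use of "either upadacitinib or one of the select systemic AD treatments at" the index date. Section 9.1 defines a new user "as not having used that specific drug substance in the year (12 months, 365 days) before the first eligible treatment". That washout is specific to the substance, so it does not fix treatment line.

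Section 9.2.1 then adds a criterion for one side: "For the potential comparator cohorts, have at least one dispensed prescription/administration of another systemic AD treatment before" the index date. It has no time limit, and there is no matching criterion for upadacitinib.

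The abstract lists the comparators: "Other select systemic AD treatments may consist of azathioprine, ciclosporin, dupilumab, methotrexate and mycophenolate mofetil". In Table 1, the row on earlier AD treatment reads "Use of AD treatments other than the ones being studied within 1 year prior to" the index date, with the categories biologic, non-biologic systemic, phototherapy and topical.

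Section 9.7.1 includes treatment experience among the things to be described: "Drug utilization and individual baseline characteristics (e.g.; demographics, comorbidities, concomitant treatments, treatment experience, healthcare utilization) will be summarized". Section 9.7.2 plans Cox models "using appropriate strategies such as IPTW, PS matching/ stratification/ adjustments or others to achieve comparable balance across cohorts". Section 9.7.2.1 adds a sensitivity analysis, within the same study population, in people with "no prior use of any of the other systemic AD treatments within 12 months from" the index date.

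**The concern.** Every comparator patient has, by rule, already had another systemic AD treatment. An upadacitinib patient may be starting a first one. Treatment line is thus tied to the exposure by the entry criteria.

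This matters because the registers hold no score-based AD severity (Section 9.9), and Section 9.7 itself groups failure of other therapies with higher disease burden. Earlier immunosuppression may also bear directly on some outcomes: Section 7 names infection and possibly skin cancer as side effects of azathioprine. If the two sides differ in treatment history and the analysis cannot see or correct the difference, part of any hazard ratio reflects history rather than drug. The comparison is conditional on finding a suitable comparator, but it is one of the primary objectives.

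**Working it through.** The protocol states no figure on this point and its study-size section is blacked out, so there is nothing to reproduce. The check is a reading of the rules followed by an illustration.

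**1. Entry rules side by side.** Comparators: 100% have an earlier systemic, by criterion. Upadacitinib: a share p may be naive, with p not given.

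**2. What this does to the propensity score.** Among people with no earlier systemic, the comparator group is empty, so the probability of being in the upadacitinib cohort is 1. Inverse-probability weighting gives these people a weight of 1/1 = 1 and has no comparator to weight up. Regression adjustment extrapolates, and a stratum of naive patients contains one treatment only. Matching or trimming can at most discard them, and does so reliably only if prior systemic use is in the score.

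**3. Whether a listed variable captures it.** The Table 1 row omits AD treatments under study. Earlier azathioprine, ciclosporin, dupilumab, methotrexate or mycophenolate, which can satisfy the comparator criterion, therefore has no specific row. The look-backs also differ: unlimited for the criterion, 1 year for the row. A score built from Table 1 alone could show good overlap while the groups differ on this point.

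**4. The sensitivity analysis.** Combining the two rules:
- Comparators: at least one other systemic at some time, none in the last 12 months, so the last one is more than 12 months old.
- Upadacitinib: none in the last 12 months, and possibly none ever.

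Recent exposure is equalised; ever-exposure is not.

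**5. Size, as an illustration.** Assumptions, none from the documents: naive share p among upadacitinib users; event rate k times as high in pretreated as in naive patients; true hazard ratio 1; no adjustment of any kind.

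Apparent ratio = ((1 − p)k + p) / k.

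For k = 1.5: with p = 10%, (0.90 × 1.5 + 0.10)/1.5 = 1.45/1.5 = 0.97; with p = 30%, (0.70 × 1.5 + 0.30)/1.5 = 1.35/1.5 = 0.90.

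| Naive share p | k = 1.25 | k = 1.5 | k = 2.0 |
|---|---|---|---|
| 10% | 0.98 | 0.97 | 0.95 |
| 20% | 0.96 | 0.93 | 0.90 |
| 30% | 0.94 | 0.90 | 0.85 |
| 50% | 0.90 | 0.83 | 0.75 |

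Standardised difference of a yes/no prior-systemic indicator, with q = 1 − p pretreated on upadacitinib and 100% among comparators: (1 − q)/√(q(1 − q)/2). For q = 90% this is 0.10/√0.045 = 0.47; for q = 70% it is 0.93; for q = 99% it is 0.14.

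**6. After the change.** With the same criterion on both sides the indicator is 100% in each cohort, its difference is 0 and the factor is 1.00. Number, type and recency of earlier systemics would still need adjustment.

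**The case against.** The protocol leaves more room than the Table 1 row suggests. Section 9.3.3 and the abstract list past and present medication use among the variables, without excluding the studied drugs. The abstract and Section 9.7.1 name treatment experience. Section 9.9 promises that confounders will be identified and adjusted for. Nothing restricts the propensity score to Table 1, and the exact covariate list is commonly left to the SAP. A reader might infer that treatment line will not be adjusted for; the protocol does not say that. What stands is that no listed variable secures it.

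The comparison is also conditional. Sections 9.1 and 9.7.1 put descriptive work and an overlap check first, and these may change the design. If prior systemic use enters the score, the lack of overlap would show there. This softens the point but does not remove it, because the criterion is fixed in this protocol and the variable that would expose the problem is not listed.

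The rule may have a sensible aim. Section 9.7 expects high-risk upadacitinib users to be more likely to have failed other therapies, so requiring pretreatment of comparators may bring the groups closer. The protocol does not state that aim, it does not cover lower-risk users, and achieving it would need the same restriction on both sides.

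Three other strong readings are tempting:
- That the hazard ratio will make upadacitinib look safer. Section 9.7 also expects upadacitinib users to differ in baseline risk factors for MACE, malignancy and VTE, and high-risk users to carry more disease burden, which may push the other way. Nor do the documents show that prior systemic treatment raises the rate of all 12 outcomes.
- That the sensitivity analysis makes matters worse. It equalises recent exposure and leaves ever-exposure unequal, so its effect is mixed.
- That treatment history is the best severity marker available. The protocol's stated proxy is healthcare utilisation, and it does not rank the two.

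**Conclusion.** The point holds as a design asymmetry that should be fixed before the comparative analyses. Three things rest on the text alone: the prior-systemic criterion binds comparators only; the Table 1 row does not capture earlier use of the studied drugs; and the sensitivity analysis inherits the asymmetry. It follows that naive upadacitinib users, if there are any, cannot be balanced by weighting or adjustment.

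The size is unknown. In the illustration the distortion is small if few users are naive (0.98 to 0.95 at 10%) and material if many are (0.94 to 0.85 at 30%). These figures assume p and k and no adjustment at all. The planned propensity-score methods, with AD inpatient days, AD outpatient visits and comorbidities as listed variables, could reduce the distortion. The direction given is that of this one mechanism when k is above 1; the net direction of confounding cannot be read from the documents. The distortion vanishes if nearly all upadacitinib users turn out to be pretreated, which the planned descriptive work could establish if prior use of the studied drugs is recorded.

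**What to change.** 1. **Section 9.2.1.** For the comparative analyses, apply the same prior-systemic criterion to both cohorts. Keep all upadacitinib users, naive or not, in the descriptive incidence.
2. **Table 1 and the propensity score.** Add number, type and recency of prior systemic AD treatments, including each studied substance, with an ever look-back beside the 1-year one. Report the naive share of upadacitinib users in the descriptive analysis.
3. **Section 9.7.2.1.** Make the sensitivity analysis symmetric: either both cohorts pretreated with no other systemic in the prior 12 months, or naive against naive with the comparator criterion lifted.

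The cost is wording in three places and variables derived from the drug and patient registers already planned for exposure. The naive-against-naive option also needs naive comparator initiators kept in the extraction. Naive here means no record in the available look-back.

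The real price is that naive upadacitinib users leave the main hazard ratio, which narrows its population and costs precision. With equal follow-up and an assumed rate ratio of 1.5, restriction removes 0.10/1.45 = 7% of upadacitinib events if 10% are naive, and 0.30/1.35 = 22% if 30% are. Because the study-size figures are blacked out, this loss cannot be set against the target.

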### The primary objectives are:

To assess comparability across upadacitinib and other select systemic treatments for AD through in-depth assessments of treatment pattern and patient disposition at baseline.

To describe the incidence of the following safety outcomes in adolescent and adult individuals with AD treated with upadacitinib:

- malignancy (excluding NMSC), including malignancy by type
- NMSC
- MACE
- VTE
- serious (in-patient) infections (incl. OI)
- HZ
- EH/ KVE
- active TB
- GI perforation
- DILI
- fractures
- all-cause mortality

If a suitable comparator is identified: to describe and compare (when feasible) the incidence of the above safety outcomes in adolescent and adult individuals with AD treated with upadacitinib, relative to those treated with other select systemic AD treatments.

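### Comparator eligibility does not tie the drug to AD, so patients treated for transplantation, leukaemia or another immune disease can enter and may raise comparator rates

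*Protocol*

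**What the plan says.** The candidate comparators are named in the abstract of the protocol: "Other select systemic AD treatments may consist of azathioprine, ciclosporin, dupilumab, methotrexate and mycophenolate mofetil". Section 8 sets the comparison for people with AD on upadacitinib "relative to those treated with other select systemic AD treatments".

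Section 9.2.1 links the drug to AD through timing. A patient must "have at least one dispensed prescription/administration of upadacitinib or one of the select systemic AD treatments within 12 months from the AD diagnosis", be a new user, be at least 12 years old and have 12 months' residency. Comparator patients have one further condition: "For the potential comparator cohorts, have at least one dispensed prescription/administration of another systemic AD treatment before" the index date. The line "The following exclusion criteria apply to the study population" is followed by a single item: "Individuals who used other JAK inhibitors (e.g. tofacitinib, baricitinib, abrocitinib) at any time (all available lookback time) before the" index date.

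Table 1 (Section 9.3.3) lists other reasons for taking these drugs as medical history within five years. They include an entry that begins "Transplantation (organ/bone marrow" and the run "Acute lymphocytic leukemia (ALL) Systemic lupus erythematosus (SLE) Polymyositis and dermatomyositis Pemphigus". Nephrotic syndrome, rheumatoid arthritis, psoriasis, Crohn's disease and ulcerative colitis are there too. No exclusion in Section 9.2.1 and no sensitivity analysis in Section 9.7.2.1 uses them, and Section 9.9 does not mention use of a comparator drug for another disease.

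**The concern.** Four of the five candidates (all but dupilumab) are general immunosuppressants, and Table 1 shows that the authors expect some users to have transplantation, leukaemia or other immune disease. Someone with an AD code who starts mycophenolate after ciclosporin because of a transplant can meet every criterion. That person then counts as AD treated with a comparator.

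If such patients have more serious infections, more deaths and (after transplantation) more new malignancies, and are commoner among comparator starters, the comparator rate reflects their other disease as well as the drug. The contrast then moves towards showing no excess for upadacitinib, which in a safety study is the direction that reassures wrongly. Crude comparator rates, planned in Section 9.7.1 if a suitable cohort is found, have no adjustment at all.

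**Working it through.** The plan gives no figure to reproduce: the study-size section is redacted, and neither the share nor the excess risk of these patients is stated. The arithmetic below only shows how the bias behaves.

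**Inputs, all assumed.** p = share of comparator starters treated for another disease; q = the same share among upadacitinib starters; k = their event rate relative to other patients; true rate ratio (RR) = 1.5.

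**1. Crude contrast, q = 0.** Comparator rate factor = 1 + p(k − 1). The RR is multiplied by the inverse.

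| p | k | Comparator factor | RR multiplied by | True 1.5 seen as |
|---|---|---|---|---|
| 1% | 5 | 1 + 0.01 × 4 = 1.04 | 0.96 | 1.44 |
| 1% | 10 | 1 + 0.01 × 9 = 1.09 | 0.92 | 1.38 |
| 2% | 10 | 1 + 0.02 × 9 = 1.18 | 0.85 | 1.27 |
| 5% | 5 | 1 + 0.05 × 4 = 1.20 | 0.83 | 1.25 |
| 5% | 10 | 1 + 0.05 × 9 = 1.45 | 0.69 | 1.03 |

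**2. Such patients in both cohorts.** Observed RR = 1.5 × [1 + q(k − 1)] / [1 + p(k − 1)].
- q = p = 5%: 1.50 for any k, so no bias.
- q = 10%, p = 5%, k = 3: 1.5 × 1.20 / 1.10 = 1.64. The bias reverses.

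**3. After weighting, cohorts of 1,000 each, q = 0.** IPTW to the combined population (average treatment effect, ATE) gives each comparator patient in the unrepresented group a weight of 1.
- p = 5%, k = 3: weighted comparator numbers are 1,950 and 50. Rate factor = (1,950 + 3 × 50) / 2,000 = 1.05, and the RR is 1.5 / 1.05 = 1.43.
- p = 10%, k = 5: (1,900 + 5 × 100) / 2,000 = 1.20, and the RR is 1.25.

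Matching or weighting to the upadacitinib population gives this group no weight, and the RR returns to 1.50.

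**4. A few such patients on upadacitinib.** If the condition is fully captured in the propensity score, both weighting schemes return 1.50 in expectation. With 1 such patient among 1,000 on upadacitinib and 50 among 1,000 on comparator, the propensity is 1/51, so under ATE weighting that one patient has a weight of 51.

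**5. What the look-back can capture.** Section 9.3.3 sets five years for medical history. A transplant recorded only before then is invisible to any propensity score built on Table 1.

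**The case against.** The strongest reply is that the protocol has more filters than its single exclusion suggests. Entry needs a new start of that substance, an AD diagnosis in a patient register and, for comparators, an earlier different systemic drug; a transplant patient continuing long-term mycophenolate fails the new-user rule. Comparators are only potential: Section 9.7.1 examines comorbidities, propensity-score overlap and standardised differences before any is used, and crude comparator rates appear only if a suitable cohort is found. Section 7 notes that AD is associated with autoimmune disease, so a blanket exclusion would remove genuine AD patients.

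Much of this stands, and it rules out stronger readings that a reader might infer:
- **That an AD code and a dispensing are enough to enter.** They are not. But the remaining criteria do not test indication, and moving between immunosuppressants for another disease satisfies the prior-drug rule.
- **That no adjustment could repair it.** Matching drops patients without a counterpart, and Section 9.7.2 allows matching. It equally allows IPTW and does not fix the target population.
- **That upadacitinib risk is certainly hidden.** Upadacitinib starters with these diseases are kept too. Section 9.7 also expects high-risk upadacitinib users to have failed other therapies and to have more disease burden, which pushes the other way. Net direction is not established.
- **That 0.96–0.69 is the error in the reported hazard ratio.** It is a crude contrast on assumed inputs; the planned hazard ratio comes from Cox models with propensity-score strategies.
- **That previous leukaemia feeds the malignancy outcome.** Table 3.3 has a five-year history exclusion for malignancy, and Section 9.3.2 discards the first 12 months, which largely closes that route. It does not stop new cancers in transplant recipients. Serious infection has only a one-year history exclusion, and none is shown for death.

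The comparability step can reject a drug, but nothing commits it to removing this group of patients from a drug that is accepted.

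**Conclusion.** The point holds as a gap in eligibility with a possible, unquantified bias. Section 9.2.1 does not restrict comparator use to AD, and no planned exclusion or sensitivity analysis addresses the gap. Crude comparator rates of serious infection, death and, through transplant recipients, malignancy may be raised. A crude or ATE-type IPTW contrast may be pulled towards no excess risk.

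The size runs from none (equal shares in both cohorts) to a crude rate ratio multiplied by 0.69 (5% of comparator starters at 10 times the rate, none on upadacitinib, no adjustment); at 1% and 5 times it is 0.96. Matching or weighting to the upadacitinib population removes the bias for captured conditions, but not for a transplant older than the look-back. The change is worth making because it is cheap and removes a group with probably little overlap, whichever method is chosen. Eligibility is fixed in the protocol, so this is not a detail that can be assumed to be left to the SAP.

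**What to change.** In Section 9.2.1, for comparator incidence rates and all comparative analyses, exclude from every cohort, upadacitinib included, patients with transplantation (all available look-back) or acute lymphocytic leukaemia before the index date. Report the number excluded by drug.

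In Section 9.7.2.1, add two sensitivity analyses:
- one that also excludes the other Table 1 conditions that are clear non-AD indications for the study drugs, named in advance (for example nephrotic syndrome, SLE, polymyositis/dermatomyositis, pemphigus, polyarteritis nodosa, rheumatoid arthritis, Crohn's disease, ulcerative colitis and psoriasis);
- one without any of these exclusions.

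Keep all upadacitinib starters with AD in the descriptive incidence, so that objective is unaffected.

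The cost is a line of eligibility text using variables already planned, plus a longer look-back for transplantation. The comparison cohorts become slightly smaller, and the comparative results will not generalise to AD patients with a transplant or leukaemia. Keeping the wider list in a sensitivity analysis avoids dropping genuine AD patients with a second immune disease from the main comparison.
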